9.2 Main analysis of the primary endpoint and ranked secondary endpoints

The following hypotheses are tested in a hierarchical order, to preserve type I error rate:

1. A lower MAP-target regimen (≥ 55 mmHg) is non-inferior to the standard MAP-target regimen ($\text{MAP} \geq 65$ mmHg) in terms of the primary endpoint of the composite of all-cause mortality and severe renal failure at 30 days.
2. A lower MAP-target regimen (≥ 55 mmHg) is superior to the standard MAP-target regimen ($\text{MAP} \geq 65$ mmHg) in terms of the primary endpoint of the composite of all-cause mortality and severe renal failure at 30 days.
3. A lower MAP-target regimen (≥ 55 mmHg) is superior to the standard MAP-target regimen ($\text{MAP} \geq 65$ mmHg) in terms of the first secondary endpoint of all-cause mortality at 30 days.
4. A lower MAP-target regimen (≥ 55 mmHg) is superior to the standard MAP-target regimen ($\text{MAP} \geq 65$ mmHg) in terms of the second secondary endpoint of days alive and out of hospital at 30 days.

All analyses are performed on an intention-to-treat (ITT) basis. The ITT population consists of all subjects who have been randomized (i.e. when the subject number and allocated regimen are recorded in the electronic case report form (eCRF)). Patients are analysed in accordance with the randomized treatment assignment irrespective of the factual implementation of the assigned treatment regimen.

Rates of primary and first secondary endpoint are estimated as the cumulative incidence at 30 days after randomization by the Kaplan-Meier method. Rate differences are defined as the rate in the index group minus the rate in the reference group.

1. Non-inferiority of the lower MAP-target regimen in terms of combined all-cause mortality and severe renal failure at 30 days is declared if the upper limit of the 95% confidence interval (CI) of the rate difference excludes 10%. This is the equivalent of non-inferiority testing with a one-sided alpha of 0.025 with a non-inferiority limit of 10%.
2. Superiority of the lower MAP-target regimen in terms of combined all-cause mortality and severe renal failure at 30 days is declared if the 95% confidence interval (CI) of the rate difference excludes 0%. This is the equivalent of superiority testing with a 2-sided alpha of 0.05.

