3. Superiority of the lower MAP-target regimen in terms of all-cause mortality at 30 days is declared if the 95% confidence interval (CI) of the rate difference excludes 0%. This is the equivalent of superiority testing with a 2-sided alpha of 0.05.
4. Superiority of the lower MAP-target regimen in terms of days alive and out of hospital at 30 days is declared if the two-sided p-value of the Mann-Whitney-U test applied to days alive and out of hospital at 30 days is lower than 0.05.

Details of the statistical analyses will be provided in the statistical analysis plan.

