Number of days that a patient spends alive and out of hospital from randomization to 30 days. Calculated by subtracting days in hospital from 30 days for every patient that leaves the hospital alive. If a patient deceases during hospital stay, the DAOH is zero. If a patient dies after hospital discharge, the number of days from their

death to 30 days is counted.

Days alive and out of ICU

Number of days that a patient spends alive and out of the ICU from randomization to 30 days. Calculated by subtracting days in ICU from 30 days for every patient that leaves the ICU alive. If a patient deceases during ICU stay, the *days alive and out of ICU* is zero. If a patient dies after ICU discharge, the number of days from their death to 30 days is counted.

Days alive and free of mechanical ventilation

Counted as 30 days minus the amount of days that a patient was mechanically ventilated. These days are counted as the difference between start date of mechanical ventilation and the date of discontinuation. If a patient was ventilated during more than one episode, the total number of days counts. If a patient dies after discontinuation of mechanical ventilation, but before 30 days, the amount of days between their death and 30 days, are also subtracted from 30.

Days alive and free of mechanical circulatory support (MCS)

Counted as 30 days minus the amount of days that a patient received any form of MCS (IABP, Impella, ECMO, LVAD). These days are counted as the difference between start date of mechanical ventilation and the date of discontinuation. If a patient was ventilated during more than one episode, the total number of days counts. If a patient dies after discontinuation of mechanical ventilation, but before 30 days, the amount of days between their death and 30 days, are also subtracted from 30.

Renal function at during hospital stay and at 1 year

Measured by creatinine ($\mu\text{mol/L}$) and expressed as estimated glomerular filtration rate (eGFR).

Time to renal replacement therapy

Time to initiation of renal replacement therapy expressed in days from randomization.

Time to peak creatinine

Time to highest creatinine-level ($\mu\text{mol/L}$) during hospitalization expressed in days from randomization.

Days alive and free of catecholamine therapy

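### Days alive and out of hospital scores in-hospital death and survival in hospital through day 30 both as zero, so the step 4 rank test ties them and loses power and clarity

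*Protocol*

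**What the plan says.** Protocol, Appendix A, defines DAOH as "Number of days that a patient spends alive and out of hospital from randomization to 30 days". Three rules follow:

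- **Discharged alive:** "Calculated by subtracting days in hospital from 30 days for every patient that leaves the hospital alive".
- **Death in hospital:** "If a patient deceases during hospital stay, the DAOH is zero".
- **Death after discharge:** "If a patient dies after hospital discharge, the number of days from their" death to day 30 is to be counted.

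No rule is written for a patient who is alive and still in hospital at day 30.

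Section 8.2 lists DAOH as the second ranked secondary endpoint. Section 9.2 introduces the testing order with "The following hypotheses are tested in a hierarchical order, to preserve type I error rate". The order is non-inferiority and then superiority on the primary composite (steps 1 and 2), 30-day all-cause mortality (step 3) and DAOH (step 4). Step 4 succeeds if the "two-sided p-value of the Mann-Whitney-U test applied to days alive and out of hospital at 30 days is lower than 0.05". The protocol leaves further analysis detail to the SAP, which was not available for this review.

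**The concern.** A rank test uses only the order of the scores, so what matters is which outcomes the score separates. Here a death in hospital and a survivor who has not yet left hospital share the lowest value. The tie correction keeps the Mann-Whitney test valid, but it does not make the ordering sensible: few would dispute that death is worse than a long admission.

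The trial's hypothesis is better survival in a condition whose mortality the introduction puts as high as 50%. If some of the patients saved by the lower target are still admitted at day 30, step 4 does not register them. The report could then say that mortality fell but DAOH did not improve, partly because of how DAOH was scored.

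**Working it through.** **1. The tie.**

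- Death in hospital on any day: score 0, by explicit rule.
- Alive and in hospital for all 30 days: 30 − 30 = 0, by the opening sentence of the definition.

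Moving a patient from the first state to the second changes no rank. Nothing else in the protocol separates the two.

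**2. The plan's own figures.** Section 9.3 gives 752 evaluable patients for 45.9% vs 35.9%, two-sided 0.05, 80% power. With unpooled variance:

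(0.459 × 0.541 + 0.359 × 0.641) × (1.96 + 0.84)² / 0.10² = 0.4784 × 7.849 / 0.01 ≈ 375.5, so 376 per arm and 752 in total.

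The figure reproduces. The protocol states no power for DAOH, so the rest needs assumptions.

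**3. Simulated power at step 4.** Inputs: 376 per arm (from the plan), Mann-Whitney at two-sided 0.05, 3,000 trials per scenario. Assumed, not in the documents: deaths 42% vs 33%, all in hospital; lognormal stay with median 13 days for patients discharged alive; still-admitted shares, reference vs index, as a percentage of all randomized patients. Share scoring zero = deaths + still admitted.

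| Still admitted | Share scoring zero | Power, plan's score | Power, death ranked lowest |
|---|---|---|---|
| 5% vs 5% | 47% vs 38% | 61% | 64% |
| 10% vs 10% | 52% vs 43% | 62% | 67% |
| 8% vs 12% | 50% vs 45% | 25% | 45% |
| 10% vs 15% | 52% vs 48% | 18% | 40% |

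Repeat runs agree within about 2 points. Across equal shares from 2% to 10% the loss is about 2 to 6 points. The second column explains the pattern: equal shares leave the 9-point mortality difference intact, while unequal shares cut it to 5 or 4 points.

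**4. The same scenarios, only among trials that pass step 3.** Plan's score vs death ranked lowest:

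- 5% vs 5%: 77% vs 81%
- 10% vs 10%: 79% vs 87%
- 8% vs 12%: 33% vs 58%
- 10% vs 15%: 23% vs 55%

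A repeat run gave gains of 4 to 9 points for equal shares and 26 to 30 points for unequal shares.

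**5. A second set of assumptions.** Deaths 45.9% vs 35.9% (the primary-endpoint rates as a stand-in), median stay 11 days, 4,000 trials, and still-admitted shares expressed as a percentage of survivors.

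- Equal shares of 5%, 10% and 20% of survivors: 65% vs 69%, 61% vs 69%, 54% vs 69%. These losses are larger than in step 3 because an equal share of survivors means more patients still admitted in the index arm; for example, 10% is 0.10 × 54.1% = 5.4% of the reference arm and 0.10 × 64.1% = 6.4% of the index arm.
- Half of the extra survivors still admitted: about 24–26% vs 46–54%.
- All extra survivors still admitted: about 5%, the alpha level, vs 22–29%.

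**6. The opposite case.** If the regimen also cuts prolonged admission, ranking death lowest lowers power from 94% to 88% overall, and by about 1 point among trials that pass step 3.

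**7. Death after discharge.** Discharge on day 10 and death on day 15 gives 15 − 10 = 5 days alive and out of hospital. Counting the days from death to day 30 gives 30 − 15 = 15, and an earlier death would score higher. This contradicts the opening sentence of the definition. It also differs from the Appendix A definitions for ventilation, circulatory support and catecholamines, which subtract those days.

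**The case against.** **The score is a correct count.** Both patients have exactly zero days alive and out of hospital, and the test is valid with ties. This stands: the tie is a weak design choice, not an arithmetic error. It does not settle the matter, because a rank test is free to order the two outcomes, and the rule for the still-admitted survivor is not written down.

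**Survival is already tested.** A reader might infer that step 4 ignores the benefit the trial seeks, or that the benefit would go unseen. The documents do not support that. Death is part of the primary endpoint, step 3 opens with "Superiority of the lower MAP-target regimen in terms of all-cause mortality at 30 days is declared if" and comes directly before DAOH, and every saved patient discharged by day 30 raises the DAOH ranks. In the equal-share scenarios the plan's score keeps about 61% power from mortality alone. However, passing step 3 does not remove the loss, as the conditional figures show.

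**The large losses are assumed.** The protocol gives no still-admitted share, no length of stay and no separate mortality rate. Nor does it say that saved patients are the ones most likely to remain in hospital. In the unequal scenarios few extra patients go home (100 − 50 = 50% vs 100 − 45 = 55%; 48% vs 52%), so part of the low power reflects a small true effect on time out of hospital. This stands, and the figures should be read as a range.

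**Lowering only in-hospital death would be inconsistent.** A patient discharged on day 5 who dies on day 20 has 15 days and would still rank above a survivor discharged on day 20, who has 10. This stands, so the fix must cover every death by day 30.

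**Conclusion.** The point holds as a minor one. Appendix A leaves the survivor still admitted at day 30 without an explicit rule, its opening sentence gives that patient 0, and the step 4 test then ties survival with in-hospital death. The tie follows from the text and needs no assumption; its cost does. That cost is about 2 to 6 points of power with equal still-admitted shares of 2% to 10% of randomized patients, and about 20 points if many saved patients are still admitted.

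A reader might also infer an inflated type I error or a threat to the primary result. Neither follows: the test remains valid, and DAOH is the last step of the hierarchy. The consequence is confined to the power of step 4 and to what a result there would mean.

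**What to change.** In Appendix A, and in the SAP to match:

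- For the rank test, score every patient who dies by day 30, in hospital or after discharge, below every survivor (for example −1).
- Score a survivor in hospital through day 30 as 0, and other survivors in days as now.
- Report mean and median DAOH in plain days beside the test. For deaths after discharge, subtract the days after death instead of counting them.

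If the tie is intended, say so, and still write the rule for the survivor in hospital through day 30 and correct the rule for death after discharge.

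The cost is a short rewrite of one definition, with no new data, best made before unblinded data are seen. There are two downsides. The tested score for the dead becomes a rank and not a count of days. Some power is also lost if the regimen mainly shortens long stays, about 1 point once step 3 is passed.

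### Read literally, the rule for deaths after discharge scores days dead as days alive and out of hospital, against the definition's own first sentence

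*Protocol*

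**What the plan says.** Section 8.2 of the protocol lists DAOH at 30 days as the second ranked secondary endpoint and refers to Appendix A for the definition. Section 9.2 makes it hypothesis 4, the last in the fixed order. Superiority is declared if the two-sided p-value of the "Mann-Whitney-U test applied to days alive and out of hospital at 30 days is lower than 0.05".

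The Appendix A definition has four parts:

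- The quantity: "Number of days that a patient spends alive and out of hospital from randomization to 30 days".
- Patients discharged alive: "Calculated by subtracting days in hospital from 30 days for every patient that leaves the hospital alive".
- Death in hospital: "If a patient deceases during hospital stay, the DAOH is zero".
- Death after discharge: "If a patient dies after hospital discharge, the number of days from their" "death to 30 days is counted" (one sentence, split by a page break).

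The definition of days alive and out of ICU, a tertiary endpoint in section 8.3, ends the same way: "If a patient dies after ICU discharge, the number of days from their death to 30 days is counted".

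The definitions for mechanical ventilation, mechanical circulatory support and catecholamine therapy treat the same interval differently. In each, "the amount of days between their death and 30 days, are also subtracted from 30".

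**The concern.** The time between death and day 30 is neither alive nor out of hospital in any useful sense. A rule that makes this interval the score rewards early death: among patients who die after discharge, each further day of survival lowers the score by one. A patient who dies just after an early discharge would rank close to a survivor, while one who dies in hospital scores zero.

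DAOH is tested confirmatorily at two-sided 0.05, so each patient needs one prespecified score. If the closing sentence stays, whoever programs the endpoint must choose between following it and following the first sentence. In an open-label trial that choice should not be left until outcome data exist.

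**Working it through.** The protocol states no figure for DAOH, so there is none to reproduce. The check is to score example patients under each reading of the text.

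**Notation.** H is days in hospital (a single admission starting at randomization, so H equals the discharge day) and D is the day of death, with D later than H.

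**Three readings for death after discharge**

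- A, closing sentence taken literally: score = 30 − D.
- B, only the rule for patients discharged alive, with no deduction for death: score = 30 − H.
- C, the interval from death to day 30 also subtracted, as in the three neighbouring definitions: score = 30 − H − (30 − D) = D − H.

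Only C equals the days actually spent alive and out of hospital, which is what the first sentence defines.

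| Discharge day | Death day | A | B | C |
|---|---|---|---|---|
| 5 | 6 | 24 | 25 | 1 |
| 8 | 10 | 20 | 22 | 2 |
| 8 | 28 | 2 | 22 | 20 |
| 10 | 12 | 18 | 20 | 2 |
| 10 | 20 | 10 | 20 | 10 |
| 10 | 29 | 1 | 20 | 19 |

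A falls by one for each extra day of survival and C rises by one. They agree only when 30 − D = D − H, that is D = (30 + H)/2; for H = 10 this is day 20. Under A, the patient discharged on day 8 who dies on day 10 scores 20. A survivor discharged on day 12 scores 30 − 12 = 18 and ranks below that patient.

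**How many patients.** The protocol gives no rate of death between discharge and day 30. If the rate were 1% to 3% (assumption), then 0.01 × 776 ≈ 8 to 0.03 × 776 ≈ 23 of the randomized patients would fall under the sentence. For deaths after ICU discharge, an assumed 3% to 8% gives about 23 to 62.

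**Effect on the Mann-Whitney test.** Two illustrative simulations used 376 patients per arm (752 evaluable / 2). All other inputs are assumptions that the protocol does not supply.

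1. 30-day mortality 44% versus 34%; gamma-distributed stay with mean about 12 days; the same share of deaths after discharge in both arms, spread evenly to day 30; 1,500 replicates.

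| Share of deaths after discharge | Power, rule A | Power, rule C |
|---|---|---|
| 2% | 67.2% | 67.1% |
| 5% | 66.9% | 66.2% |
| 10% | 67.3% | 67.4% |
| 20% | 62.5% | 61.6% |

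2. Mean stay about 12.5 days. With equal arms and 1% to 3% of patients dying after discharge, type I error was about 5% under both rules. With in-hospital mortality 33% versus 43% and 2% dying after discharge in each arm, power was 68% under both. In a deliberately lopsided case (3% versus 1%, all within five days of discharge), moving from C to A raised the rejection rate from 5.4% to 6.6% near the null and from 65% to 70% under a large effect.

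**The case against.** The strongest defence is that the closing sentence does not say the days after death are credited. It says they are counted, and in this appendix that word is also used for days that go into the deduction: in the ventilation definition, all ventilated days over several episodes count toward what is removed from 30. Read with the first sentence and the neighbouring definitions, the authors may have meant that the days after death join the days subtracted. That is a plausible intention, but it is not written. The two definitions that use this wording lack the explicit subtraction that the other three have, and the repetition in the ICU definition makes a single slip of the pen less likely.

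A reader might infer that hypothesis 4 as a whole is scored backwards. The protocol does not support that. The reversal is one reading, though the literal one, and it concerns only patients who die between discharge and day 30. Survivors and in-hospital deaths are scored as intended, and a few post-discharge deaths receive the same score either way.

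A reader might also infer that the arm with more early post-discharge deaths would win the test. That needs an imbalance for which the protocol gives no basis, and even the lopsided example moved the rejection rate by only 1.2 and 5 percentage points.

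Section 9.2 leaves analysis details to the SAP, which was not available here. This does not remove the point, because section 8.2 sends the reader to Appendix A for the definition and the rule stated there is faulty.

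**Conclusion.** The point holds as a defect in a stated definition. Taken literally, the closing sentence contradicts the first sentence of the same definition and the treatment of the same interval in three neighbouring ones. For an individual patient the error can be large: 18 days in either direction in the day-8 example (20 against 2, and 2 against 20).

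For the trial the consequence is limited. Hypothesis 4 is the last test in the hierarchy, so no later confirmatory test depends on it. The primary endpoint, the mortality test and the sample size are unaffected, and the ICU endpoint is tertiary. The effect on the Mann-Whitney result is probably small unless deaths after discharge are frequent or differ between arms. That judgement rests on simulations with assumed lengths of stay and death rates, and the patient counts rest on assumed rates too. The reason to correct the text is that a confirmatory endpoint needs one unambiguous and valid score per patient; no material loss of power or inflation of type I error under plausible balanced conditions has been shown.

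**What to change.** In the DAOH definition, replace the closing sentence with one stating that, if a patient dies after hospital discharge, the days from death to day 30 are also subtracted from 30. In the definition of days alive and out of ICU, make the same replacement, worded for death after ICU discharge. Keep the existing rule that death during the stay scores zero, and carry the same wording into the SAP.

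Nothing further is needed for this point. In particular, a general formula that nets off readmission days should not be added in passing: for a patient who dies during a readmission it could give a positive score where the retained zero rule gives zero.

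The cost is one sentence in each of two Appendix A definitions. No new data are required and the sample size does not change. The correction should be made before any DAOH data are analysed by arm.

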8.3 Tertiary endpoints *(for definitions, see Appendix A)*

The tertiary endpoints are:

- Days alive and out of ICU (30 days)
- Cardiovascular death at 1 year
- Enzymatic infarct size
- Lactate clearance (mean + area under the curve 0-36 hours)
- Days alive and free of mechanical ventilation (30 days)
- Days alive and free of mechanical circulatory support (30 days)
- Severe renal failure requiring renal replacement therapy (at 30 days, 1 year)
- Renal function (during hospital stay and 1 year)
- Time to peak creatinine (hospital stay)
- Time to renal replacement therapy
- Days alive and free of catecholamine therapy (30 days)
- Vasoactive inotropic score (VIS) (during hospital stay)
- Time to hemodynamic stabilization (hospital stay)
- Blood pressure and heart rate during the first 24 hours
- Hemodynamic parameters (during ICU / CCU admission)
- Arrhythmias during hospital admission
- Major vascular complication during admission (bleed or thrombo embolic event)
- Infection / sepsis during hospital admission
- Myocardial re-infarction within 30 days
- Left ventricular ejection fraction (at day 3, before hospital discharge, and at 1 year)

- Neurological outcome (at 30 days and 1 year)
- Protocol adherence / use of bail-out therapy
- Hospital readmission for cardiac reason within 1 year

The cost-effectiveness endpoints are:

- Health-related quality of life based on the EQ-5D-5L questionnaire at 12 months
- Resource utilization based on iMTA Medical Consumption (iMCQ) and iMTA Productivity Cost Questionnaire (iPCQ) (at 30-day, 3-month, 6-month and 1-year follow-up)

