Counted as 30 days minus the amount of days that a patient received any type of catecholamine. These days are counted as the difference between start date of catecholamine therapy and the date of discontinuation. If a patient received catecholamine therapy during more than one episode, the total number of days counts. If a patient dies after discontinuation of catecholamine therapy, but before 30 days, the amount of days between their death and 30 days, are also subtracted from 30.

Time to hemodynamic stabilization

Earliest time by which the patient is hemodynamically stable and receives no catecholamine therapy, expressed in amount of days, counted from randomization.

Blood pressure and heart rate

As measured by (non-)invasive hemodynamic monitoring, reported hourly.

Hemodynamic parameters

Cardiac index (L/min/m²), pulmonary capillary wedge pressure (mmHg), right atrial pressure (mmHg), pulmonary artery pressure (mmHg) and pulmonary artery pulsatility index every 8 hours during the first 48 hours of admission.

Arrhythmias during admission

Type	Definition
Atrial	Atrial flutter, tachycardia or fibrillation
Ventricular	Monomorphic or polymorphic VT greater than 30 seconds or hemodynamically unstable ventricular arrhythmia requiring intervention, or VF.

Vasoactive inotropic score

Dopamine dose ($\mu\text{g}/\text{kg}/\text{min}$) +
 Dobutamine dose ($\mu\text{g}/\text{kg}/\text{min}$) +
 100 x Epinephrine dose ($\mu\text{g}/\text{kg}/\text{min}$) +
 10 x milrinone dose ($\mu\text{g}/\text{kg}/\text{min}$) +
 10.000 x vasopressin dose (U/kg/min) +
 100 x norepinephrine dose ($\mu\text{g}/\text{kg}/\text{min}$)

Ischemic complication during admission

Type	Definition
Acute limb ischemia	
Rutherford I	Limb viable, not immediately threatened
Rutherford IIa	Limb marginally threatened, salvageable if promptly treated
Rutherford IIb	Limb immediately threatened, salvageable with immediate revascularization
Rutherford III	Limb irreversibly damaged, major tissue loss or permanent nerve damage inevitable
Mesenteric ischemia	As proven by mesenteric angiography, CT angiography, pathology or based on high clinical suspicion. (Suspicion might arise in critically ill patients with abdominal pain or distension requiring vasopressor support and evidence of multi-organ dysfunction.)

Thromboembolic event during admission

Deep venous thrombosis, pulmonary embolism, cerebrovascular event.

Major bleed during admission

Major bleed	

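### Appendix A does not limit the ventilation-, MCS- and catecholamine-free day counts to randomisation to day 30, and it removes days after death only if support had already stopped

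*Protocol*

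**What the plan says.** Protocol section 8.3 names the three tertiary endpoints with a 30-day label: "Days alive and free of mechanical ventilation (30 days"), "Days alive and free of mechanical circulatory support (30 days") and "Days alive and free of catecholamine therapy (30 days"). It refers to Appendix A for their definitions.

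Appendix A gives the counting rules:

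- Ventilation: "Counted as 30 days minus the amount of days that a patient was mechanically ventilated".
- MCS: "Counted as 30 days minus the amount of days that a patient received any form of MCS (IABP, Impella, ECMO, LVAD").
- Catecholamines: "Counted as 30 days minus the amount of days that a patient received any type of catecholamine".

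In each case the days to subtract are the interval between starting and stopping, added up over episodes. For catecholamines, for example: "If a patient received catecholamine therapy during more than one episode, the total number of days counts". The days between death and day 30 are also subtracted, but only for a patient who dies after the support has been discontinued and before day 30. In the MCS paragraph, the sentences on start and stop dates, repeat episodes and death all speak of mechanical ventilation.

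The neighbouring definition of days out of ICU does state its window: "Number of days that a patient spends alive and out of the ICU from randomization to 30 days". Days out of hospital is worded the same way. Both give zero for a death during the stay.

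**The concern.** The label promises a count that runs from randomisation to day 30 and must lie between 0 and 30. The operational rule does not deliver that, for three reasons.

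- Support before randomisation or after day 30 is subtracted from 30 as if it fell inside the window.
- The death rule covers only one of the ways in which a patient can die before day 30. Death while on support, and death in a patient who never had the support, both leave the days after death in the score as if they were days alive and free of it.
- The MCS count cannot be derived from MCS dates as the text stands.

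A programmer who follows Appendix A would produce scores that contradict the endpoint's name, and some early deaths would look like good outcomes. At stake are three tertiary endpoints that describe how much organ and circulatory support each regimen required.

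**Working it through.** The plan states no figure for these endpoints, so there is none to reproduce. The check applies the Appendix A rule to illustrative patients. Their support and death days are assumptions. Day 0 is randomisation, and for a death on support the stop date is taken as the day of death. For the LVAD rows, MCS dates are used in place of the ventilation dates in the text.

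Rule as written: score = 30 - sum of (stop - start) over episodes. A further (30 - day of death) is subtracted only if the patient dies before day 30 and after discontinuation.

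Rule limited to the window: score = E - support days between day 0 and E, where E is day 30 or the day of death, whichever comes first.

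| Illustrative patient | As written | Limited to the window |
|---|---|---|
| Survivor, support days 0-20 | 30 - 20 = 10 | 30 - 20 = 10 |
| Survivor, support days 0-30 | 30 - 30 = 0 | 30 - 30 = 0 |
| Survivor, support days 0-40 | 30 - 40 = -10 | 30 - 30 = 0 |
| Survivor, episodes on days 0-5 and 35-38 | 30 - 5 - 3 = 22 | 30 - 5 = 25 |
| Survivor, LVAD days 20-45 | 30 - 25 = 5 | 30 - 10 = 20 |
| Survivor, LVAD from day 20, still in place | no stop date: undefined | 30 - 10 = 20 |
| Off support day 5, died day 10 | 30 - 5 - 20 = 5 | 10 - 5 = 5 |
| Support from day -1 to day 5, died day 6 | 30 - 6 - 24 = 0 | 6 - 5 = 1 |
| Died on support day 2 | 30 - 2 = 28 | 2 - 2 = 0 |
| Died on support day 10 | 30 - 10 = 20 | 10 - 10 = 0 |
| Died day 3, never had the support | 30 - 0 = 30 | 3 - 0 = 3 |

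The table shows three things:

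1. The two rules agree when all support lies inside the window and any death comes after support has stopped. A negative score needs more than 30 support days in total. Support after day 30 can still distort a positive score, as in the 22 against 25 and the 5 against 20.
2. The death rule causes errors that have nothing to do with long support. A death on support at day 2 scores 28, and a survivor who needed 20 days scores 10. A death at day 3 without the support scores the maximum of 30. Section 5.4 allows MCS only as bail-out therapy, so deaths without any MCS are to be expected. The documents do not say how many.
3. Support before randomisation does occur: section 4.3 admits patients already on drugs to maintain systolic pressure. Its effect should be small, because section 4.4 excludes shock with onset more than 12 hours earlier.

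**The case against.** The best defence is that the window is evident. Section 8.3 labels all three endpoints as 30-day endpoints, the counts start from 30, and the death clause refers to day 30. The hospital and ICU definitions also subtract days from 30 without an explicit floor, so the phrase about randomisation to day 30 does all the work there, and the label might do the same here. This stands as evidence of intent. It does not settle the scores, because section 8.3 sends the reader to Appendix A for the definition and the rule there departs from the label. Nor does the label touch the death clause or the ventilation dates in the MCS paragraph.

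It could also be argued that death ends support and so counts as discontinuation, which would bring the day-2 death to 30 - 2 - 28 = 0. The text does not say so, and that reading still leaves a death without any support at the maximum.

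Section 9.4 leaves the tertiary analyses to the SAP, which may refine the derivation. An SAP that did so would still have to depart from the definition fixed here.

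A reader might infer more than the documents support:

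- *That every long-supported survivor or LVAD recipient scores below zero.* A negative score needs more than 30 support days; an LVAD in use from day 20 to day 45 scores 5.
- *That an LVAD kept for a year gives a hugely negative score and drags down an arm mean.* A device still in place has no discontinuation date, so its score is undefined rather than negative. Table 1 marks mechanical support under ICU stay only. No mean-based analysis is specified: section 9.1 summarises skewed variables by median and interquartile range.
- *That the repair stops any survivor from ranking below a death.* A survivor supported throughout the window scores 0, and a patient off support at day 5 who dies at day 10 scores 5, under the corrected rule too. Any count of days alive and free of support has this property.

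**Conclusion.** The point holds as a minor one. The three definitions state a rule that, followed literally, gives wrong scores: -10 instead of 0 for support on days 0-40, 5 instead of 20 for an LVAD on days 20-45, no score for a device still in place, and 28 instead of 0 for a death on support at day 2. The MCS paragraph also refers to the wrong dates.

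The sizes rest on illustrative patients and a literal reading of Appendix A. How many patients would be affected cannot be taken from the documents; catecholamine therapy is the least likely of the three to run past day 30. All three endpoints are tertiary and lie outside the hierarchical tests of section 9.2, so the primary and ranked secondary conclusions do not change.

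**What to change.** In Appendix A, replace the counting rule in all three definitions with one text, for example: *number of days from randomization to day 30 on which the patient is alive and free of the support; support before randomization or after day 30 is not counted; days after death count as zero, whether or not support had been discontinued or ever given; range 0 to 30*.

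In the MCS definition, replace the ventilation dates with MCS start and stop dates, and count a device in place at day 30 up to day 30. A cap at day 30 alone would not be enough, because it leaves the scores of patients who die on support, or without it, unchanged.

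The cost is a short rewording of three definitions. No new data are needed: the present rule already relies on start, stop and death dates. The SAP derivation should use the same text.
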